The device will not be made available to patients who do not choose to participate in the study.

9. Upload any supporting tables or documents (e.g. protocol documents, figures/tables, data collection forms, study communications/reminders):

Upload ALL instruments/guides that will be used or that participants will experience (i.e. see, hear, complete), including measures, scripts/questions to guide interviews, surveys, questionnaires, observational guides, etc.:

Upload ALL recruitment and screening materials, including such as ads, flyers, telephone or in-person scripts, letters, email invitations, TelegRAM announcements, and postcard reminders, screening scripts, screening forms, and screening measures:

ID: MS1_HM20021188

View: SF2 - Project Details

Project Details

1. * Select all of the following types of interventions that apply to this study (selections will branch):

- Social/Behavioral interventions or experimentation / Tasks / Environmental manipulations
- Deception (misleading participants through false or incomplete information)
- Drug(s) / Biologics / Supplement(s) / Other Compounds (investigational products or products whose administration is dictated by the study protocol and not per the physician's clinical judgment)
- Placebos
- Safety and/or effectiveness evaluation of Bio-Medical Device(s), including in-vitro diagnostic devices/assays, mobile medical apps, and HUDs used in clinical investigations**
- Washout Periods
- Expanded Access - Treatment Use of an Investigational Product
- Medical or Surgical Procedures (eg: physical exam, clinical procedures, scans, etc)**

- Specimen/biological sample collection
- None of the Above

2. * Select all of the following types of interactions that apply to this study (selections will branch):

- Surveys / Questionnaires /Written responses to questions (including data entry)**
- Active Internet data collection (i.e. using the internet to interact or intervene directly with research participants)
- Interviews / Focus Groups / Verbal responses to questions
- Audio / Video recording or photographing participants
- Observations**
- Passive Internet data collection (i.e. passively observing online behavior)
- Educational Settings/Assessments/Procedures
- None of the Above

3. * Select all types of secondary information and/or specimens that apply to this study (selections will branch):
See the help text for definitions.

- Individually Identifiable Health Information (PHI or RHI)**

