- * Describe the risks of each research procedure to participants or others. For each identified risk, provide an assessment of the anticipated seriousness and likelihood of the risk. Some examples of possible risks include but are not limited to:
 - Physical risks (e.g. bodily harms or discomforts, side effects, etc.)
 - Psychological risks (e.g. emotional, mental, or spiritual harms or discomforts, changes to thoughts, beliefs, or behaviors, etc.)
 - Research data risks (e.g. loss of confidentiality and privacy)
 - Social or legal risks (e.g. impacts on relationships or reputation, legal or criminal justice actions for self or others, etc.)
 - Financial risks (e.g. impacts on income, employability, or insurability, loss of services, etc.)
 - Other risks (e.g. unforeseeable risks of experimental procedures, risks related to particular study designs (randomization, washout, placebo, withholding care/services, deception), etc.)

See the help text for additional guidance.

Device may become damaged, risking battery burns if left near exposed skin. Settings may fail resulting in too much or too little water irrigation.

Patients may be self conscious concerning wearing the tubing when others may see it.

Patients may fear being identified for health-related oral dryness, resulting in psychological discomfort.

Length of pilot study may be too long or too short to gain insightful data.

There is a risk of a loss of confidentiality, which frequently occurs in studies in which patients with specific health conditions are recruited and followed.

The oral irrigation device involves risks that are currently unknown or unforeseeable.

- * Describe how each of the risks/harms/discomforts identified above will be minimized:

Instructions to be given orally and in written print out format.

Study may have to be repeated or an addendum requesting extending the study if deemed necessary.

Study activities (recruiting and survey completion) will occur in private dental treatment areas to protect subject privacy.

Patients and their electronic health records assigned to the School of Dentistry are protected under HIPPA.

Patient is allowed to discontinue the study at any time for any reason, and may discontinue use of device during the study for up to 6-8 hours periods of time if necessary.

3. * Describe any potential risks or harms to a community or a specific population based on study findings (e.g. information that could be stigmatizing or derogatory):

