No risk to the community.

4. Where appropriate, discuss provisions for ensuring necessary medical, professional, or psychological intervention in the event of adverse events to the subjects:

Patients may discontinue participation at any time for any reason.

If battery burn occurs, discontinue use, seek medical attention to site of burn, and inform investigators immediately.

Water flow settings can be adjusted. If too much or too little water is flowing through tubing, contact investigators immediately for instructions for adjustment or discontinue use and return to clinical setting for water flow to be adjusted by investigator.

5. * Describe criteria for when the investigator would withdraw an individual participant from the study; such as safety or toxicity concerns, emotional distress, inability to comply with the protocol, etc.:

If patient is not willing or capable of following protocol and instructions, and demonstrates behavior that may result in harm due to misuse of the device, that patient will be withdrawn.

6. * Summarize any pre-specified criteria that would trigger the investigator/sponsor/monitoring committee to stop or change the study protocol due to safety concerns:

Any unforeseeable issues with the safe and proper operation of the device would trigger the discontinue of or change in the study protocol.

Data and Safety Monitoring

Data and safety monitoring is a system for checking the study's data at regular intervals over the study period to identify and address issues that could affect the safety of research participants. This requirement is in accordance with 45 CFR 46.111.

The purpose of data and safety monitoring plan is to set forth study team procedures for monitoring/addressing:

- Participant safety (physical, psychological, etc.)
- Data validity
- Early stopping (termination) based upon changes in risks and benefits.

7. * Indicate if this study will have a Data Safety Monitoring Board (DSMB) or a Data Safety Monitoring Plan (DSMP): [Required for all greater than minimal risk studies]

DSMB

DSMP

No DSMB/DSMP [Note: This response is not applicable for greater than minimal risk studies]

ID: MS1_HM20021188

View: SF2 - Privacy

Privacy

Privacy refers to an individual's right to control how others view, record, or obtain information about them. When privacy is violated it can involve such things as

- Being asked personal questions in a public setting;

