6. * If "other protections" was selected in one or more of the questions above, specify where this study's paper and electronic research data and/or physical specimens will be stored and how they will be secured from improper use and disclosure.
Not applicable7. * If research data that contains any of the 18 HIPAA identifiers will be released to person(s) or group(s) outside of the VCU study team or the PI's department, identify the data recipient(s) along with their VCU department or other institutional or organizational affiliation(s).
Not applicable

8. * Select all identifiers that will be collected as part of this study (including for recruitment, data gathering, data analysis, etc.), even if the data will eventually be anonymized:

- Names**
- Geographic Locators Below State Level
- Social Security Numbers
- Dates (year alone is not an identifier)
- Ages over 89 (age under 89 is not an identifier)
- Phone Numbers
- Facsimile Numbers
- E-mail Addresses
- Medical Record Numbers**
- Device Identifiers**
- Biometric Identifiers
- Web URLs
- IP Addresses
- Account Numbers
- Health Plan Numbers
- Full Face Photos or Comparable Images
- License/Certification Numbers
- Vehicle ID Numbers
- Other Unique Identifier
- No Identifiers
- Employee V#

9. * If the study will code (i.e. de-identify) the research data by replacing subjects' names with assigned subject IDs, explain the following aspects of the coding process:

- The process for how subject IDs will be generated/assigned (e.g. random, sequential)
- Whether there will be a key that links the subject ID with direct identifiers.

If a key will be created, describe

- The place where the key will be stored
- The role(s) of all individuals who will have access to the key
- When the key will be destroyed

See the help text for guidance.

A study code will be created to ensure the ability to link the study data from the two survey timepoints and to track the devices assigned to the patients and ensure they are returned. Subjects will be assigned a sequential identifier (Subject 1 through Subject 25). The study key will contain the subject's dental record number, contact information, and unique identifier. This is necessary as it will allow for the PI to contact any subjects who do not return with the device and to link subject data from subsequent visits. The study data (survey responses, salivary flow rate data) will be de-identified. No attempts will be made to re-identify the study data.

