1. * Has this human subjects protocol (not the grant application) already been reviewed by the funder of a sponsored project (e.g. a federal, state or non-profit funding sponsor)?

Yes

No

16. Upload any documents requested in the questions above:

ID: MS1_HM20021188

View: SF2 - HIPAA

HIPAA

HIPAA Privacy Board Requirements

For guidance, see <https://www.vcuhealth.org/our-story/who-we-are/compliance-services/compliance-services>

1. * Select the source of the Individually Identifiable Health Information. See help text for definitions.

- PHI associated with or derived from (i.e. obtained from or entered into) VCU Health medical records or VCU Dental Care records
- Research Health Information (RHI) created or received by a study and kept solely in study records (e.g. self reported or the result of research tests and not entered into health records)
- PHI associated with or derived from (i.e. obtained from or entered into) a non-VCU HIPAA covered entity's health records

2. * Summarize the types of health information that will be obtained or used in this research. Do not describe only the identifiers that you will collect or use during the study.

Patients medical and dental history, salivary flow rates, and surveys that measure oral dryness and effects on quality of life due to oral dryness will be obtained at the start and end of the study.

3. * Describe the source(s) of the protected health information (e.g. which clinical databases):

The dental school stores the medical and dental history electronically in Axiom; this is where the information will be obtained, in addition to reviews of this information completed at time of appointments.

4. * Does the PI certify that this study's access to and use of the protected health information is limited to the minimum amount necessary to be able to effectively conduct the research?

Yes No

5. * Select all pathways this research will employ to use or access PHI (selections will branch):

- De-Identified Data (none of the 18 identifiers are recorded or associated with the research data)
- Limited Data Set
- Waiver of Authorization
- Partial Waiver of Authorization (temporary waiver for recruitment purposes and/or waiver of some elements of Authorization)
- Signed Authorization Combined with Consent Form
- Signed Authorization as Stand-Alone Form

ID: MS1_HM20021188

View: SF2 - Partial Waiver of Authorization

Partial Waiver of Authorization

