1. * Select the purpose for requesting the partial waiver of authorization:

Identify possible participants to recruit for the study

Waive some elements of authorization (such as signature)

2. * Explain how the partial waiver of authorization poses no greater than minimal risk to participants' privacy: *(Alternative question phrasing: How do the risk(s) of this use of identifiable health information compare to the risks to privacy a person might reasonably experience in normal everyday life?)*.

The use of patient PHI for screening is temporary and accessed through our informatics system, and full authorization will be sought from participants who consent, so the use of patient PHI for screening presents no more than minimal risk to participants.

Screening information will be obtain through our informatics system/department. The risks are mitigated through the use of identifiers and contact information that is either password or VPN protected by the university.

3. * If you selected "Identify possible participants to recruit" above, describe when will the 18 HIPAA identifiers be destroyed for those who do not eventually enroll in the study?

Following Participant Contact

Upon Reaching Study Accrual Objectives

Other

4. * Since Other was selected above, describe when identifiers will be destroyed for those who do not eventually enroll in the study.

The patient dental records contain the identifiers. The identifiers used in the study will be destroyed at the end of the study.

5. * Other than the PI and research personnel identified in this research application, who else will have access to the Protected Health Information?

The student doctor, or doctors, who treat the patient in our clinic.

6. * Explain why the study cannot practicably be conducted without the partial waiver of authorization: *(Alternative question phrasing: Why is this partial waiver necessary to make the study achievable or viable?)*

The use of identifiers will allow us to narrow the patients contacted for the study, in effort to find patients who would qualify. This eliminates the need for screening a potentially larger population of patients clinically, while allowing for more patients who qualify to be added to the study over a shorter time span.

7. * In applying for a partial waiver of authorization, the PI agrees to the following:

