- Lead Student/Trainee Investigator (leading their own project)
-
- Research Coordinator
-
- Research Nurse
-
- Consultant
-
- Research Assistant
-
- Pharmacist
-
- Statistician
-
- Regulatory Coordinator
-
- Trainee/Student(working on project)**
-
- Other
-
- N/A: Requesting Waiver of Consent

7. * Describe the consent procedures used for this group. Include when, where, and how consent / assent will be obtained both initially and, if applicable, during ongoing participation in the study:

At time of clinical and survey determination of inclusion.

For ongoing purposes, the patient will be informed to contact either the PI or the care provider through email, phone or text, or during other non-study related treatment in the clinical setting, to inform of their desire to return the device and discontinue participation in the study.

8. * Describe the process for minimizing any potential perception of undue influence to participate when there is a pre-existing relationship between the participant and the researcher (e.g. treatment provider/patient; instructor/student; supervisor/employee, etc.):

Patients will be allowed to end participation at any time. Patients who do not consent to participation will receive instructions for how to care that are standard for patients with xerostomia.

9. * How much time will participants be given to make a decision:

Patient is seated upright in the treatment chair and at eye level with PI who will give a brief description of the study.

The care provider for the patient will be in the cubicle with the PI and patient at all times. After explanation of the study, the care provider will then finish the consent process in the absence of the PI.

Patient may also take a copy of consent and decide after days of consideration, or until participant capacity is met.

10. If applicable, describe the procedures for consenting children upon entering adulthood or participants who

are no longer decisionally impaired:

Not applicable; no children will be recruited to participate.

ID: MS1_HM20021188

View: Personnel

Personnel

1. * Name:

[name]

2. * Is this individual a 'COI Investigator'?

Conflict of Interest (COI) Investigator - any individual who has a level of independence and responsibility comparable to that of the PI for the design, conduct, or reporting of research.

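### Harms and device malfunctions reach the study only if patients volunteer them; no supplied section provides for asking about, logging or summarising them

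*Protocol*

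**What the plan says.** **Risks.** Protocol, Risks, Discomforts, Potential Harms and Monitoring, item 1, names battery burns, self-consciousness about visible tubing and fear of being identified as having dry mouth. On water flow it says: "Settings may fail resulting in too much or too little water irrigation". It then adds: "The oral irrigation device involves risks that are currently unknown or unforeseeable".

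**Reporting and trigger.** Item 4 of the same page tells a patient with a burn to notify the investigators at once. A patient with too much or too little flow is to contact them, or to stop and return to the clinic for adjustment. Item 6 gives the safety trigger: "Any unforeseeable issues with the safe and proper operation of the device would trigger the discontinue of or change in the study protocol".

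**Data.** HIPAA, item 2, lists medical and dental history and salivary flow. It also says that "surveys that measure oral dryness and effects on quality of life due to oral dryness will be obtained at the start and end of the" trial. Data Confidentiality and Storage, item 9, answering a question about coding, says: "The study data (survey responses, salivary flow rate data) will be de-identified".

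**Aims, visit and analysis.** The aims are OHIP-14, XI, salivary testing and CODS. Study Procedures, item 6, has one return visit at 4-6 weeks, for re-examination and the survey. The SAP compares scores before and after use of the device.

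**Stopping participation.** Under Consent Groups, item 7, "the patient will be informed to contact either the PI or the care provider through email, phone or text" when wishing to withdraw and return the device.

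**The concern.** The protocol expects harms of kinds it cannot yet name and makes the study's continuation depend on noticing them. Yet the only described way to notice them is for a patient to make contact, and the instructions to do so cover two foreseen problems: burns and wrong flow. The trigger concerns unforeseeable issues, for which no reporting instruction or standard enquiry is described.

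Study Population, item 3, says the pilot should supply estimates for sizing a larger study if one is justified. A follow-up study of a device worn day and night would also want to know how often it faulted, how often it caused a problem and why patients stopped. Harms not asked about at the only follow-up visit cannot reliably be recovered later.

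**Working it through.** No figure in the documents bears on this point, so the main check is a reading of each place where safety data could enter.

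| Place | Content | Enquiry, log or summary of harms or malfunctions? |
|---|---|---|
| Background, item 3, and Study Procedures, item 2 (aims) | OHIP-14, XI, saliva, CODS | None stated |
| Study Procedures, item 6 (visit) | Re-examination and survey at 4-6 weeks | None stated |
| HIPAA, item 2 (information obtained) | History, flow, dryness and quality-of-life surveys | None stated |
| Data Confidentiality, item 9 | Surveys, flow | None stated; not exhaustive, since CODS is missing |
| Documents list | One patient questionnaire; no adverse-event, malfunction or withdrawal form | None listed |
| Risks, item 4 | Patient contacts investigators about a burn or wrong flow | Spontaneous route only; no log, definition or assessor |
| SAP | Before/after tests of scores | None stated |

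The quality-of-life items listed under direct benefits attribute each problem to the teeth, the mouth or a denture. They would not isolate embarrassment caused by the device.

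**What systematic asking would give.** Inputs: n = 25 is the maximum in Study Population, item 1, and the top subject number in Data Confidentiality, item 9. The true per-patient risks p are assumptions, because the documents give none. All 25 are assumed to receive a device and to be asked.

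Chance of at least one event = 1 - (1 - p)^25:
- p = 1%: 1 - 0.99^25 = 22.2%
- p = 2%: 1 - 0.98^25 = 39.7%
- p = 5%: 1 - 0.95^25 = 72.3%
- p = 10%: 1 - 0.90^25 = 92.8%

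Upper 95% limit after 0/25:
- one-sided: 1 - 0.05^(1/25) = 11.3%
- two-sided exact: 1 - 0.025^(1/25) = 13.7%

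**Effect of incomplete reporting.** If only half of events were volunteered (an assumption), p is replaced by p/2 and the four chances become 11.8%, 22.2%, 46.9% and 72.3%. The true reporting fraction is unknown, so no valid upper limit can be attached to an absence of volunteered reports.

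**Fewer patients assessed.** The 25 is a ceiling that also counts people screened and consented. With 20 assessed (assumed), the chance at p = 5% is 64.2% and the limits after zero events are 13.9% and 16.8%. With 15, they are 53.7%, 18.1% and 21.8%.

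**The case against.** The strongest reply is that this is a small pilot of a marketed device used as indicated, with effectiveness and quality-of-life aims, and that it never promises a safety report. Much of that stands, and it rules out several stronger readings.

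- **That the trigger has no input.** Not supported: the protocol routes burns and flow faults to the investigators, who could act on them. The weakness is reliance on volunteered reports, with no definition, log or assessor.
- **That the selected intervention type commits the study to a safety evaluation.** The option reads "Safety and/or effectiveness evaluation of Bio-Medical Device(s), including in-vitro diagnostic devices/assays", and effectiveness alone satisfies it. The case rests on the risk statement and the trigger.
- **That the data phrase in the coding answer lists everything collected.** It omits CODS, a stated aim. The visit description, HIPAA summary and SAP are better evidence.
- **That none of the named risks has a data field.** The REDCap form, consent and device guide were not supplied, so this cannot be asserted. The DSMB/DSMP selection is not legible either.
- **That a report made to the care provider is lost.** Partial Waiver of Authorization, item 5, names "The student doctor, or doctors, who treat the patient in our clinic" as having access in addition to research personnel. But student dentists ask survey questions and collect saliva, and the care provider completes the consent process. The PI can also contact patients who do not return the device. What is missing is a written duty to pass on a problem or a reason for stopping.

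History-taking and re-examination at the end could bring a burn or a visible injury to light. That is incidental detection and gives no denominator of patients asked.

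**Conclusion.** The gap is real but bounded. Burns and wrong flow have a spontaneous route to the investigators. Nothing supplied provides for a standard enquiry, a log or a descriptive summary of harms and malfunctions. The undefined trigger therefore depends on what patients choose to report, and the pilot cannot give the larger study a harm or malfunction rate.

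The size is modest even when repaired: with 25 patients all asked, zero events would still leave risks of up to 11.3% (one-sided) or 13.7% (two-sided) not excluded. The gain is that such a limit could be stated at all. These figures rest on all 25 receiving a device and answering. The conclusion would change if the REDCap form already contains the questions; the SAP would then still lack the summary.

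The change should be made because it is cheap and the information cannot be collected afterwards.

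**What to change.** First check the REDCap follow-up form. Unless it already does so:

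1. Add a short standard block, completed at the existing 4-6 week visit and at any contact in which a patient reports stopping. Ask yes/no for burn, too much or too little flow, self-consciousness about the device, fear of being identified, and any other problem, each with a brief description, plus the reason for stopping.
2. State that whoever receives a report of a problem or a stop, including the care provider, passes it to the PI for entry in a log.
3. Add one SAP sentence: number and percent of patients with each event, with exact 95% intervals, over all patients given a device, stating how many were asked.

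The cost is a few minutes of patient time, one table and a minor IRB amendment; no visit is added. If event dates are recorded, the amendment should also check the identifier list in Data Confidentiality and Storage, item 8, where dates do not appear to be marked in the text available. None of this sets a clinical rule; it only makes what happens countable.
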